## 6.2. Serious Adverse Events

An SAE is any untoward medical occurrence that meets any of the following criteria:

- Results in death.
- Is immediately life-threatening (refers to an event in which the participant is at risk of death at the time of the event; it does not refer to an event, which hypothetically might have caused death if it were more severe).
- Requires inpatient hospitalization or prolongation of existing hospitalization.
- Results in a persistent or significant incapacity or substantial disruption of the ability to conduct normal life functions.
- Is a congenital anomaly/birth defect.
- Based on appropriate medical judgment, represents an important medical event that may jeopardize the participant or may require intervention to prevent 1 of the other outcomes described above.

### 6.2.1. Clarification of Serious Adverse Event Definition

- Death is an outcome of an SAE and not an SAE in itself. When death is an outcome, the event(s) resulting in death should be reported (e.g., “pulmonary embolism” with a fatal outcome). The appropriate diagnosis or term should be recorded and assigned severity Grade 5.
- In instances of death due ultimately to the underlying disease, the cause of death should be indicated as the specific event or condition resulting in death to the extent possible. If no appropriate term with a Grade 5 severity in the CTCAE can be identified, then a term should be selected from the CTCAE category “death.”
- “Life-threatening” means that the participant was at immediate risk of death from the event as it occurred. This does not include an event that might have led to death if it had occurred with greater severity. Grade 4 events (e.g., thrombocytopenia) are not always serious unless they have life-threatening consequences or result in hospitalization.
- Preplanned or elective hospitalizations, including social and/or convenience situations (e.g., respite care), are excluded from SAE reporting. In addition, “admissions” under 23-hour Observation or Emergency Room visits are excluded from SAE reporting; however, such events should still be reported on the appropriate eCRF page.
- Overdose of either SYNB1934v1 (defined as a total dose  $\geq 2 \times 10^{13}$  live cells in a 24-hour period) or concomitant medication without any overdose signs or symptoms unless the event meets SAE criteria (e.g., hospitalization) are excluded from SAE reporting; however, such events should still be reported on the appropriate eCRF page.
- SAEs that occur within the safety follow-up period but are related to subsequent therapies are excluded from SAE reporting:
  - Participants who have completed study dosing or who terminate from study and then undergo subsequent therapies during the safety follow-up period and experience an SAE specifically related to the administration of the subsequent therapy will not have those events reported as SAEs. This exclusion will include “elective” hospitalizations necessary for the administration of such therapies.

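### Protocol 6.2.1 excludes Emergency Room visits and 23-hour observation admissions from SAE reporting without limiting this to the hospitalization criterion, so some events that are serious under 6.2 could go unreported as SAEs

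*Protocol*

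**What the plan says.** Protocol Section 6.2 gives the definition: "An SAE is any untoward medical occurrence that meets any of the following criteria". Six criteria follow. Only one is inpatient hospitalization or its prolongation. The others include an event that "Is immediately life-threatening (refers to an event in which the participant is at risk of death at the time of the event", an event causing persistent or significant incapacity, and an event that, on medical judgment, "represents an important medical event that may jeopardize the participant or may require intervention to prevent 1 of the other outcomes described above". None of these three refers to where the participant was treated.

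Section 6.2.1 is headed as a clarification of that definition. One of its bullets begins: "Preplanned or elective hospitalizations, including social and/or convenience situations (e.g., respite care), are excluded from SAE reporting". The next sentence of the same bullet adds that admissions (the protocol puts the word in quotation marks) "under 23-hour Observation or Emergency Room visits are excluded from SAE reporting; however, such events should still be reported on the appropriate eCRF page". It has no exception.

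The following bullet, on overdose, does have one. Overdoses "without any overdose signs or symptoms unless the event meets SAE criteria (e.g., hospitalization) are excluded from SAE reporting".

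The SAP tabulates SAEs in Section 3.15.1.5 but gives no SAE definition of its own, so it inherits whatever the protocol means.

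**The concern.** A site deciding whether to send an SAE report after a participant has been seen in an Emergency Room will look at Section 6.2.1, find that encounter excluded from SAE reporting, and may stop there. Nothing in the sentence sends the reader back to the other criteria in Section 6.2.

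SAE status determines several things:

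- the 24-hour report to the sponsor for any event that is not an AESI (Protocol 6.4);
- in practice, how soon the sponsor can assess whether a reaction is serious, unexpected and suspected, and so needs expedited notification (Protocol 6.2.2);
- SAP summary tables J (SAEs), K (SYNB1934v1-related SAEs) and L (PPI-related SAEs).

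The setting makes the case realistic. Participants prepare their doses at home (Protocol 4.3.3), and most visits may take place away from the clinic (Protocol Table 5, note b). An acute event may therefore be treated in an Emergency Room that is not the study site. Protocol 1.7 describes the programme as having had no treatment-related SAEs, so one omitted event would bear on that statement.

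**Working it through.** No arithmetic applies beyond counting criteria. The check sets the provisions side by side.

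**1. Which criteria are exposed.** Section 6.2 lists six. One is hospitalization, which the disputed sentence may legitimately clarify. Two others have provisions of their own: death (its own bullets in 6.2.1, and a halt for a related death in 3.4) and congenital anomaly (pregnancy reporting and follow-up in 6.5). That leaves 6 − 1 − 2 = 3 criteria with a practical gap: life-threatening, incapacity and important medical event.

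**2. Two readings of the sentence.**

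- *Literal:* an event handled only through an Emergency Room visit or observation admission is outside SAE reporting. This contradicts the any-criterion rule in 6.2.
- *Contextual:* the encounter alone is not an inpatient hospitalization, and the other criteria still apply. This agrees with 6.2, but the limit is not written down.

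**3. What the rest of 6.2.1 suggests.** Three features favour the literal reading:

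- The overdose bullet, next in the list, carries an explicit exception; this sentence does not.
- The last bullet excludes from SAE reporting events that it itself calls SAEs (those related to therapy given after study dosing). So in this section the phrase can remove events that already satisfy 6.2.
- The sentence sends the events to an eCRF page, which looks like an alternative reporting route and not a definition of hospitalization.

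Two features favour the contextual reading:

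- The sentence follows one about types of hospital stay, and it uses the word admissions.
- An earlier bullet says "Grade 4 events (e.g., thrombocytopenia) are not always serious unless they have life-threatening consequences or result in hospitalization", which keeps life-threatening consequences as a separate route to seriousness.

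The text does not settle the matter.

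**4. What the other safeguards catch.**

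| Provision | What it covers | What it leaves |
|---|---|---|
| AESI reporting (6.3, 6.4) | 24-hour notice, serious or not, of hypersensitivity or infection due to SYNB1934v1 and of Grade 3 or higher GI events | Non-GI events other than these, and PPI reactions |
| Individual discontinuation (3.5) | Grade 3 or higher AEs related to IMP are a listed reason, whatever their SAE status | Concerns dosing; gives no 24-hour notice |
| Stopping rule 1 (3.4) | Grade 3 or higher AEs related to SYNB1934v1, in two or more participants | Single events, PPI-related events, individual notice |
| eCRF record (6.2.1, 10.1) | The event is still recorded | Data entry is expected within 5 business days of a participant visit, not within 24 hours of awareness |

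No row gives 24-hour notice of a non-AESI event. A life-threatening PPI reaction treated and discharged from an Emergency Room is an example: it is not an AESI, it does not count toward stopping rule 1, and it is what SAP table L is meant to count.

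**The case against.** The strongest reply is that 6.2.1 only clarifies 6.2 and nowhere claims to override it. On that view the bullet concerns which hospital encounters count as hospitalization. Its sentence on elective stays has no exception either, yet nobody would use it to exclude a life-threatening event arising during an elective stay. The exception in the overdose bullet shows little, because that bullet concerns an exposure without symptoms and not a type of encounter. The phrase about 23 hours may also mean observation status, not any care lasting less than 23 hours.

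Much of this stands. The contextual reading is reasonable and may be what was intended. It still has to be supplied by the reader, and the last bullet of 6.2.1 uses the same exclusion for events that are SAEs.

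Two stronger inferences are tempting and are not supported:

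- *That such events would be recorded as non-serious.* No provision tells an investigator to classify them so, and 6.2 still makes them SAEs. The supportable statement is that they could be omitted from SAE reporting.
- *That all five non-hospitalization criteria are overridden.* Death and congenital anomaly have their own provisions, and nothing in 6.2.1 says that it displaces 6.2.

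Nor should a product-related anaphylactic reaction be the leading example. As a hypersensitivity AESI it reaches the sponsor within 24 hours whether or not it is called serious. Expedited notification under 6.2.2 remains the sponsor's or its designee's duty under regulatory requirements, whatever 6.2.1 says; the risk there is late or missing information, not a removed obligation.

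**Conclusion.** The sentence is wrong as written: it excludes a class of encounters from SAE reporting when the most that 6.2 allows is to say that they are not, by themselves, hospitalizations. The consequence is a possibility, not a certainty. A life-threatening, incapacitating or important medical event that is not an AESI could be left out of the 24-hour report and of SAP tables J, K and L, with expedited assessment delayed or missed.

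This rests on one assumption, that at least some sites would follow the sentence literally. SAE completion instructions outside these documents might prevent that, but they cannot be checked here. With no rate of Emergency Room visits or observation stays in the documents, the number of affected events cannot be estimated. The effect is confined to safety reporting and SAE counts.

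**What to change.** Reconcile Sections 6.2 and 6.2.1 by replacing the disputed sentence with wording such as: *An Emergency Room visit or an admission under 23-hour observation does not by itself meet the hospitalization criterion. An event that meets any other criterion in Section 6.2 is reported as an SAE wherever it was treated; otherwise it is recorded on the appropriate eCRF page.* The overdose bullet already supplies a model: "unless the event meets SAE criteria (e.g., hospitalization) are excluded from SAE reporting".

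Carry the same wording into the eCRF and SAE completion guidelines. The SAP needs no change, because its SAE tables follow the protocol definition. The cost is one clause in the protocol, the matching edit to the guidelines, and a few more SAE reports.

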### 6.2.2. Serious, Unexpected, Suspected Adverse Reactions

In accordance with regulatory requirements, the sponsor or designee will immediately notify regulatory authorities and the investigators, who will in turn notify their IRB/REB as necessary, of any AE associated with IMP administration or study procedures that is a serious, unexpected, suspected adverse reaction or any finding from tests in laboratory animals that suggests a significant risk for human participants, including reports of mutagenicity, teratogenicity, or carcinogenicity. An AE or suspected adverse reaction is considered “unexpected” if it is not listed in the Investigator’s Brochure or is not listed at the specificity or severity that has been previously observed.

### 6.3. Adverse Events of Special Interest

An adverse event of special interest (AESI), whether serious or nonserious, is one of scientific and medical concern specific to SYN1934v1 for which ongoing monitoring and rapid communication by the investigator may be appropriate. Based on current preclinical and clinical data, the following AEs will be considered AESIs and should be reported to the Sponsor within 24 hours of awareness.

Adverse events of special interest for SYN1934v1 are as follows:

- Hypersensitivity reactions due to SYN1934v1.
- Infections due to SYN1934v1.
- Grade  $\geq 3$  gastrointestinal AEs per protocol specified grading criteria, including nausea, vomiting, diarrhea, and abdominal pain.

### 6.4. Reporting of Adverse Events

All AEs, serious and nonserious, will be fully documented on the appropriate eCRF. For each AE, the investigator must provide its duration (start and end dates or ongoing), intensity, assessment of causality, and whether specific action or therapy was required.

All AEs occurring from the time a participant signs the ICF through the safety follow-up period and at least one month following the last dose of SYN1934v1 must be recorded on the eCRF.

All AESIs and SAEs, regardless of relationship to SYN1934v1 or ██████████, must be reported to the Sponsor/designee on the applicable eCRF form within 24 hours of awareness. In addition, AESI or SAE forms should be uploaded and submitted to [[contact]](mailto:[contact]) within 24 hours of awareness. All AESIs and SAEs, regardless of relationship to study drug, will be followed by the Investigator until satisfactory resolution or the Investigator deems the SAE to be chronic or stable. After the final follow-up visit, only IMP-related AEs/SAEs need to be collected and reported.

### 6.5. Pregnancy

Women of childbearing potential must have a negative serum pregnancy test at screening. A urine pregnancy test will be taken at timepoints outlined in the Schedule of Events ([Table 5](#) and [Table 6](#)) and must be negative. Women of childbearing potential must agree to use acceptable methods of contraception, after informed consent, throughout the study, and for a minimum of 2 weeks after dosing has been completed. Breastfeeding women or those planning to become pregnant are excluded from the study.

If a participant becomes pregnant during the study, treatment must be discontinued. The pregnancy must be reported to the Sponsor/designee and the IRB/IEC/REB. The applicable eCRF and pregnancy report form should be completed within 24 hours of awareness by clinical site staff. Pregnancy report forms should be sent to [[contact]](mailto:[contact]). Follow-up evaluation of the pregnancy, fetus, and child should be performed. If the participant chooses to continue the pregnancy, then her pregnancy should be followed to term and 3 months after delivery, so that any important safety information can be obtained.

Males participating in the study do not need to take specific precautions to prevent pregnancy.

## 6.6. Clinical Laboratory Abnormalities

It is the responsibility of the investigator to assess the clinical significance of all abnormal laboratory values as defined by the appropriate reference ranges. All abnormal values assessed to be of clinical concern and at least possibly related to IMP or of uncertain causality should be repeated. Persistent abnormal values and changes of possible clinical concern that remain within the normal range should be followed at the discretion of the investigator.

An abnormal laboratory value that is not already associated with an AE is to be recorded as an AE if an action on IMP dosing is made as a result of the abnormality, if intervention for management of the abnormality is required, or at the discretion of the investigator.

## 6.7. Review of Safety Data

The DMC, investigator, and sponsor medical monitor will be responsible for the ongoing review and evaluation of safety data, including AEs, clinical laboratory data, and any other safety evaluations, for the duration of the study. Details will be provided in the DMC charter.

The first DMC meeting will occur when [REDACTED] have completed the DEP or when the [REDACTED] beyond the DEP baseline visit, whichever occurs first.

The DMC will also meet after the [REDACTED] participants have completed the DEP and when the last participant has completed the RWP.

All meetings will be used to review safety, to ensure that there is an adequate responder rate for the RWP primary analysis population, and to evaluate the DEP baseline Phe values of the population prior to treatment. The sponsor will remain blinded to the subject-level blood-Phe levels; however, the DEP overall responder rates and DEP baseline Phe values as well as the interim analysis results will be provided to the sponsor by the DMC.

## 7. ESTIMANDS

The following are the descriptions of the estimands for the primary and key secondary endpoints in the study, based on the methods described in ICH-E9 (R1).

### 7.1. Part 1: Primary and Key Secondary Efficacy Objective Estimands

The estimands corresponding to the Part 1 DEP primary and key secondary objectives and endpoints are described in [Table 8](#) and [Table 9](#), respectively.

**Table 8: Estimand for the Part 1 Primary Objective**

Objective	To assess the percentage change in blood Phe level
A. Population	The population is the DEP full analysis set (defined in Section 8.2) characterized by the inclusion/exclusion criteria provided in Section 4.2.
B. Variable	Continuous variable: Percent change from DEP baseline in blood Phe level at the last measurement of the iTD of SYNBI934v1

C. Intercurrent events	
 
Participant does not reach an iTD or iTD dose is dropped: As described in Section 3.1, the participant's iTD will be the highest dose tolerated. Additionally, as described in Section 8.12, doses may be dropped at the DEP interim analysis. A principal stratum approach will be taken in that the target population is the set of participants who reach an iTD and the corresponding dose is not dropped at the interim analysis.
 
Treatment discontinuation: If a participant permanently discontinues study drug in the DEP, the participant will be asked to have an early termination visit 30 days after last dose of study drug (see Section 3.5). Treatment discontinuation will follow the principal stratum approach in that if the participant has reached an iTD (defined as having reached an iTD if they tolerate 3 weeks at a dose, regardless of whether other doses are tolerated) the participant will be included in the analysis.
 
Antibiotic use: consistent with a treatment-policy strategy, antibiotic use will not be considered (i.e., all observed data will be used regardless of antibiotic use).
 
Prohibited medication use: consistent with a treatment-policy strategy, prohibited medication use will not be considered (i.e., all observed data will be used regardless of prohibited medication use).
 

D. Population-level summary	The population-level summary is the least-squares mean for the percent change from baseline in blood Phe level at the last measurement of the iTD of SYNBI934v1 derived from an MMRM using an observed case approach. The MMRM model is described in Section 8.4.1.

DEP = dose-escalating, open-label period; iTD = individually titrated dose; MMRM = mixed model with repeated measures; Phe = phenylalanine.

**Table 9: Estimands for the Part 1 Key Secondary Objectives**

Objective	To assess the absolute change in Phe level
A. Population	The population is the DEP full analysis set (defined in Section 8.2) characterized by the inclusion/exclusion criteria provided in Section 4.2.
B. Variable	Continuous variable: Change from DEP baseline in blood Phe level at the last measurement of the iTD of SYNBI934v1
C. Intercurrent events	
 
Participant does not reach an iTD or iTD dose is dropped: As described in Section 3.1, the participant's iTD will be the highest dose tolerated. Additionally, as described in Section 8.12, doses may be dropped at the DEP interim analysis. A principal stratum approach will be taken in that the target population is the set of participants who reach an iTD and the corresponding dose is not dropped at the interim analysis.
 
Treatment discontinuation: If a participant permanently discontinues study drug in the DEP, the participant will be asked to have an early termination visit 30 days after last dose of study drug (see Section 3.5). Treatment discontinuation will follow the principal stratum approach in that if the participant has reached an iTD (defined as having reached an iTD if they tolerate 3 weeks at a dose, regardless of whether other doses are tolerated) the participant will be included in the analysis.
 
Antibiotic use: consistent with a treatment-policy strategy, antibiotic use will not be considered (i.e., all observed data will be used regardless of antibiotic use).
 
Prohibited medication use: consistent with a treatment-policy strategy, prohibited medication use will not be considered (i.e., all observed data will be used regardless of prohibited medication use).
 

D. Population-level summary	The population-level summary is the least-squares mean for the change from baseline in blood Phe level at the last measurement of the iTD of SYNBI934v1 derived from

	an MMRM using an observed case approach. The MMRM model is described in Section 8.5.1.
Objective	To determine the responder population
A. Population	The population is the DEP full analysis set (defined in Section 8.2) characterized by the inclusion/exclusion criteria provided in Section 4.2.
B. Variable	Dichotomous variable: $A \geq 20\%$ reduction from baseline in blood Phe level at any time in the DEP
C. Intercurrent events	
 
Participant does not reach an iTD or iTD dose is dropped: As described in Section 3.1, the participant's iTD will be the highest dose tolerated. Additionally, as described in Section 8.12, doses may be dropped at the DEP interim analysis. A principal stratum approach will be taken in that the target population is the set of participants who reach an iTD and the corresponding dose is not dropped at the interim analysis.
 
Treatment discontinuation: If a participant permanently discontinues study drug in the DEP, the participant will be asked to have an early termination visit 30 days after last dose of study drug (see Section 3.5). Treatment discontinuation will follow the principal stratum approach in that if the participant has reached an iTD (defined as having reached an iTD if they tolerate 3 weeks at a dose, regardless of whether other doses are tolerated) the participant will be included in the analysis
 
Antibiotic use: consistent with a treatment-policy strategy, antibiotic use will not be considered (i.e., all observed data will be used regardless of antibiotic use).
 
Prohibited medication use: consistent with a treatment-policy strategy, prohibited medication use will not be considered (i.e., all observed data will be used regardless of prohibited medication use).
 

D. Population-level summary	The proportion of participants meeting the $\geq 20\%$ reduction from baseline in blood Phe level at any time in the DEP will be summarized along with 95% confidence intervals.

DEP = dose-escalating, open-label period; iTD = individually titrated dose; MMRM = mixed model with repeated measures; Phe = phenylalanine.

